## Sample Size

Sample size was calculated using G\*Power v.3.1.9.7 on repeated measure ANOVA given  $\alpha=0.05$ , moderate effect size (0.25), power of 80%, two groups with 2 measurements, correlation among repeated measures (0.50), a total sample size of 98 will be required. A total sample size of n=49 for intervention group and n=49 for control group is sought.

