## Study Design

The purpose of this study is to see if Bergamot, an aroma therapy essential oil, has any effect on comfort, ease, and stress. Participants will be asked to use a bergamot aroma inhaler, which is a small tube about the size of a lipstick container, at least three times a day for one week. Comfort, ease, and stress will be measured with self-report survey at the beginning and at the end of the week. In addition, participants will be asked to complete a daily logbook to record use of the inhaler. The study lasts for one week (7 days). The aims of this study are to explore the effects of Bergamot essential oil on comfort, ease, and stress in adults in a SUD treatment program, and to evaluate the feasibility of this type of aroma therapy intervention.

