## Objectives

Purpose:

The purpose of the study is to examine the effect of an aromatic intervention using bergamot essential oil on comfort, ease, and stress in adults in a SUD recovery program.

Primary Objectives & Aims:

The innovation of this study is to use bergamot essential oil to improve perception of comfort and ease and reduce stress among the marginalized population in a SUD recovery program in rural Appalachia.

Specific Aim #1: Pilot test bergamot essential oil intervention with adults in a substance use disorder recovery program.

**Hypothesis 1a:** Participants in the intervention group will report higher scores on comfort and ease than those in the control group.

**Hypothesis 1b:** Participants in the intervention group will report lower scores in stress than those in the control group.

Specific Aim #2: Evaluate the feasibility and acceptability of an aromatherapy intervention by examining recruitment, enrollment and retention rates, intervention fidelity, and cost analysis.

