## Statistical Analysis Plan

Data analysis For Aim 1, Descriptive (frequencies, means, ranges, standard deviations) and bivariate analysis will be conducted on the demographics, GCQ, Ease measure, and DASS scales. Statistical assumptions (i.e., normal distribution and homogeneity of variances etc.) will be tested. Sample demographics of patients will be reported. Fisher's exact test will be used for categorical variables; Repeated measures ANOVA and paired t-test will be used for continuous variables. Pearson's and Spearman's correlation analyses will be used to explore relationships among variables (Pallant, 2020). The statistical significance is set at a 5% (alpha = 5%). All analyses will be completed using Statistical Package for the Social Sciences (IBM SPSS).

For Aim 2, Descriptive statistics will be used to analyze Aim 2a. Participant recruitment, enrollment, and retention rates will be tabulated and reported. Reasons for non-participation and attrition will be recorded and will be used to develop strategies to address this. For Aim 2b, adherence to the intervention protocol will be calculated from responses in the logbooks. For Aim 2c, to determine the cost of the intervention implementation, all charges related to implementation are calculated. This includes costs of personnel time for administering each session, the materials, and incentives.

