## Prior to opening a Study Packet

1. In a private location, Enroller will determine eligibility for this study.
  - a. Inclusion criteria are as follows:
    - i. Older than 18 years of age
    - ii. Currently enrolled in treatment
    - iii. Have completed intensive phase 1 and wish to continue with treatment
    - iv. Alert & oriented
    - v. Able to provide written consent
    - vi. Able to read & write English
  - b. Exclusion criteria are as follows:
    - i. Diagnosed with severe mental illness
    - ii. Medical history of asthma
    - iii. Other serious respiratory disease
    - iv. Known allergy to citrus
2. In a private location, Enroller will prescreen using created survey tool (appendix A)
  - a. Use the prescreening survey provided
  - b. Read prescreening survey to participants and record answers
  - c. If not contraindicated by prescreening questions, allow participant to smell the aroma inhaler (3 inches from nose)
    - i. Record all reactions, “liked the smell”, “sneezed”, “said ‘yuck’” on the presurvey. Record “no negative reactions” as applicable (This is a vital component of aromatic research)
3. IF PARTICIPANT IS INELIGIBLE, thank them for their time, note on MLS that they were screened and why they were ineligible. Use the special section at the end of the MLS to make this notation. Do not use an Id # space. Write “ineligible” and the date across the top of the survey.
4. IF PARTICIPANT IS ELIGIBLE, file prescreening form in predetermined place and obtain a study packet in the order they are arranged (001-098)
  - a. Enter date and name of participant on the **Random Number Table (RNT)** sheet
5. Record Unique Identifier packet number on **Master Log Sheet (MLS)**
  - a. Use MLS to track Participants
  - b. This Unique Identifier number is already on every document in each packet

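### The 98 participants are sized for a group effect averaged over pre and post; for a moderate day-7 difference power is 29% (group main effect) or 69% (time×group), not the stated 80%

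*Combined protocol and SAP*

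**What the plan says.** The Sample Size section specifies repeated-measures ANOVA in G*Power at alpha 0.05 with "moderate effect size (0.25), power of 80" per cent. It continues: "two groups with 2 measurements, correlation among repeated measures (0.50), a total sample size of 98 will be required". It then splits the total equally: "n=49 for intervention group and n=49 for control group is sought". It does not say which repeated-measures option (between, within, or within-between interaction) was chosen.

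The Statistical Analysis Plan section says "Repeated measures ANOVA and paired t-test will be used for continuous variables". It does not name the effect (group, time or time×group) that decides the hypotheses, and it does not mention baseline-adjusted analysis.

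Hypothesis 1a, under Objectives, reads: "Participants in the intervention group will report higher scores on comfort and ease than those in the control group". Hypothesis 1b is the matching statement for lower stress.

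The two measurements are described under Study Design: "Comfort, ease, and stress will be measured with self-report survey at the beginning and at the end of the week". The enrolment steps place the pre-surveys at enrolment and start the intervention on the participant's next full day.

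On numbers available, step 4 of Prior to opening a Study Packet tells the enroller to "obtain a study packet in the order they are arranged (001-098"). No dropout allowance is given.

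**The concern.** A treatment effect can appear only in the second of the two measurements, because the first is taken before the inhaler week begins. A calculation for the group main effect assumes the difference is present in the average of both. If 98 came from that option, the stated 80% power applies to a day-7 effect twice the size that the word moderate suggests. The hypotheses concern whether the intervention arm scores better than control, which in this design means after the week.

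If the paragraph stands, a null result could be reported as coming from a trial with 80% power for a moderate effect when no repeated-measures test named in the plan has that power. The plan also leaves open which ANOVA effect decides the hypotheses, so a reader cannot tell which power figure applies.

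**Working it through.** **Inputs from the documents.** f = 0.25, power 80%, 2 groups, m = 2 measurements, r = 0.50, N = 98 and 49 per arm (Sample Size). Alpha is 5% (Statistical Analysis Plan); sidedness is not stated, but an F test with 1 numerator df is equivalent to a two-sided t test. For two groups, f = 0.25 corresponds to a standardised difference d = 2f = 0.50.

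**Step 1: reproduce 98.** Power comes from the noncentral F distribution with 1 and N − 2 df.

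- Between factors (group main effect): λ = f²·N·m / (1 + (m − 1)r).
  - N = 96: λ = 0.0625 × 96 × 2 / 1.5 = 8.00, power 0.799.
  - N = 98: λ = 0.0625 × 98 × 2 / 1.5 = 8.17, power 0.808.
  - So 98 is the smallest balanced total that reaches 80%, an exact match.
- Within-between interaction (time×group): λ = f²·N·m / (1 − r).
  - N = 34: λ = 0.0625 × 34 × 2 / 0.5 = 8.50, power 0.807.
  - So this option needs 34, and at N = 98 its power would be 0.998.
- The within-factor option also gives 34. The alternative interaction scalings λ = f²N and λ = f²(N − 2) give 128 and 130. A simple two-group comparison with d = 0.5 gives 128.

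Only the between-factors option returns 98.

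**Step 2: what that option assumes.** It takes a 0.5 SD difference between arms in the mean of pre and post. With no expected difference at pre and a difference δ at day 7, the difference in the mean is (0 + δ)/2 = δ/2. Setting δ/2 = 0.5 SD gives δ = 1.0 SD.

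**Step 3: power for a 0.5 SD day-7 difference.** Assumptions: 49 per arm, equal SDs, no baseline difference, r = 0.50. λ = (difference / SD)² × 49/2.

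| Test | Difference (SD units) | SD of the quantity compared | λ | Power | N per arm for 80% | Smallest day-7 difference at 80% power |
|---|---|---|---|---|---|---|
| Group main effect | 0.25 | √((1 + r)/2) = 0.866 | 2.04 | 29% | 190 | 0.99 SD |
| Time×group (change) | 0.50 | √(2(1 − r)) = 1.00 | 6.125 | 69% | 64 | 0.57 SD |
| ANCOVA on pre-score (95 df) | 0.50 | √(1 − r²) = 0.866 | 8.17 | 81% | 49 | 0.50 SD |

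A simulation of 8,000 runs gave 0.300, 0.689 and 0.808 for the three tests. At r = 0.50 a comparison of day-7 scores alone has the same power as time×group, 69%.

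**Step 4: sensitivity to the correlation** (same 0.5 SD at day 7, 49 per arm).

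| r | Group main effect | Time×group | ANCOVA |
|---|---|---|---|
| 0.3 | 33% | 54% | 73% |
| 0.5 | 29% | 69% | 81% |
| 0.7 | 26% | 89% | 93% |

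Time×group reaches 80% at r of about 0.62.

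**Step 5: loss.** The documents give no rate, so 10% and 20% are assumptions. They leave 98 × 0.9 = 88.2 and 98 × 0.8 = 78.4 participants.

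| Assumed loss | Group main effect | Time×group | ANCOVA |
|---|---|---|---|
| 10% | 27% | 64% | 76% |
| 20% | 24% | 59% | 71% |

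**The case against.** The strongest reply is that no sum in the Sample Size section is wrong: 98 is exactly what G*Power returns for one legitimate option. That is true. The fault is a mismatch between the effect that was powered and the hypothesis. It is also true that the option is inferred, because the section does not name it, but none of the other options tried returns 98.

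Second, the section never defines moderate as 0.5 SD at day 7. If 0.25 were G*Power's interaction f, power at 98 would be 99.8%. But that reading implies a 1.0 SD day-7 difference and a required total of 34, so it neither produces 98 nor describes a moderate effect.

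Third, 29% belongs to a test the plan does not name as deciding; time×group is the natural test in a two-arm pre/post design. This is fair, and 69% is the figure to use under that reading. It still falls short at the plan's own correlation, though it would not at r above about 0.62.

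Fourth, Aim 1 is called a pilot and Aim 2 concerns feasibility. Even so, Aim 1 carries directional hypotheses and the section makes an explicit 80% power claim, which ought to be true.

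Finally, the missing dropout allowance is separate from the choice of effect, and the plan says only that reasons for attrition will be recorded. The numbered packets also come from the in-person procedure, whereas the 2022 amendment in Appendix G moved to mailed materials. These points limit the attrition argument but leave the main one untouched.

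**Conclusion.** The concern holds. The figure of 98 matches the group main effect calculation exactly, and that calculation does not support 80% power for a moderate difference after the week. At the plan's own r = 0.50, with 49 evaluable per arm, no baseline difference, equal SDs and a two-sided 5% test, power for 0.5 SD at day 7 is 29% by group main effect and 69% by time×group. The main-effect shortfall barely depends on the correlation. The time×group shortfall does, and it disappears at higher values. The same 98 participants would give 81% under ANCOVA, so the number itself can be defended, but only with an analysis the plan does not specify and only if nobody is lost.

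**What to change.** Rewrite the Sample Size paragraph for the between-arm difference at day 7, stating the effect in SD units.

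- **Preferred:** name ANCOVA (day-7 score on arm plus pre-survey score) as the powered test in both Sample Size and Statistical Analysis Plan. State that 98 evaluable participants give about 81% power for 0.5 SD at r = 0.50. Adopting ANCOVA adds an analysis to the plan, but it uses only data already collected.
- **If repeated-measures ANOVA is kept:** name time×group as the deciding test and state 69% power for 0.5 SD, or 0.57 SD as the smallest difference detectable with 80% power.
- **In either case:** give power at the number of post-surveys expected back, with the assumed loss rate stated. For ANCOVA this is 76% at 10% loss and 71% at 20%.

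The cost is SAP wording only, with no extra participants. The stated power becomes less favourable once loss is included.

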## Data Safety Monitoring

Data safety will be maintained throughout the study. All information about participants will be stored in a locked cabinet inside a locked office. All electronic data will be stored on a password encrypted computer.

## Safety Monitoring & Unanticipated Event Reporting

This study involves use of an aroma inhaler. This study is only minimal risk because it involves aroma of a citrus essential oil named Bergamot. This essential oil is impregnated on a pure cotton wick within a manufacturer-sealed aroma inhaler. Participants are instructed and will demonstrate back to the researcher that they will use the inhaler in the prescribed fashion.

Participants encounter odors and aromas during daily life and the anticipated magnitude of harm or discomfort anticipated in the research is not greater in and of itself than those ordinarily encountered in daily life or during the performance of routine physical or psychological examinations or tests.

Participants will have an informational session with a Registered Aromatherapist, [name], who will demonstrate use and care of the aroma inhaler.

The following reminder is provided in writing for participants.

\*(When not in use, recap to close & store in a cool, dry place away from children and pets) It is OKAY to keep your closed inhaler in your pocket or purse and at room temperature ☺  
Do not tamper with the packaging. Keep out of reach of children and animals. If you develop any adverse reactions such as a headache, stop, recap inhaler, and retry a little later. If unpleasant effects, such as headache continue, discontinue use and contact [name], Co-Investigator at [[contact]](mailto:[contact])

Every effort has been made to ensure the safety of all Participants and those at the study site.

1. Aroma inhalers are factory sealed
2. Tamper resistant packaging is used
3. Safety data sheets are available online and on site
4. Inhalation of essential oils such as Bergamot is considered low risk
5. Specific instructions are provided
6. A Registered Aromatherapist created and manages this study

Participants will be instructed to seek medical care if needed and are able to withdraw from the study at any time without any repercussions. Participants are already in the care of medical staff.

## Study Duration & Timeline

Task	March to June 2022	May to June 2022	August to December 2022	January to March 2023	April to May 2023
Create grant documents	X				
Finalize & refine grant application and submit	X				
Submit proposal to WVU IRB, make revisions as needed		X			
Complete BMED research & recruitment form			X		
Enrollment & run study			X		
Complete enrollment & run data				X	
Dissertation defense & graduate					X

## Informed Consent Process

Participation in this study is contingent upon informed and ongoing consent by each adult participant. They are free to withdraw from the study at any time without any repercussion. The following pieces of data will be collected including:

### **Will collect the following listed data**

Name  
Email address  
Telephone number

### **Plus, the following**

#### **Data will be collected from the chart and from survey (self-report)**

1. Identifier variables of Comfort, Ease, and Stress
2. Stage of treatment in the SUD treatment program (Chart)
3. Presence of anxiety and/or depression (Chart)
4. Presence of severe mental illness Dx (Chart)
5. Allergies to citrus fruits such as grapefruit, lemon, orange, or bergamot (Chart and self report)

6. Previous experience with any integrative or complementary therapies such as yoga, massage, acupuncture, aromatherapy with essential oils, herbal preparations, meditation, mindfulness practices (Self-report)
7. Pregnant and/or nursing (Self-report)
8. Severe breathing problems such as asthma, chronic bronchitis, or COPD (Chart and self-report)
9. Report of sense of smell (self-report)
10. Dx of a problem with sense of smell (Chart and self-report)
11. Current illness with cold, flu, or covid (Self-report)

## Informed Consent Process

See Appendix F

## Confidentiality & Privacy

Subjects in this research study will not be anonymous but all study participant data and information will be de-identified. Upon enrollment, participants will be given a unique identifier by which all study materials will be identified. A master spreadsheet will be maintained to identify each participant by name with their unique identifier. All study data will be kept securely in a locked office.

Data will be kept for a minimum of 3 years. Electronic data will be destroyed using appropriate data deletion methods to ensure data cannot be recovered. Paper documents will be destroyed by shredding and other methods as specified by WVU procedures.

No Federal Certificate of Confidentiality is used for this study.

## Other Considerations

There are no conflicts of interest to report for the PI, [name], or Co-I's, [name], and [name]

The results of this work could be published or presented without any participant identifiers.

Other research purposes include reviewing the safety and feasibility of the aromatic intervention and developing a better understanding of disease, improving the design of future clinical trials.

## Supplies Available for Enrolling Participants (Kept in Locked Office):

1. Supply of prescreening surveys
2. Master Log Sheet (MLS) for recording Participant name and number
3. Master Random Number Table (RNT) for randomization
4. Tote with Study Packets (including surveys\*)
5. Extra forms
6. Aroma inhalers\*\*

\*Surveys Used in this Study (See Appendix A)

Surveys in this study include:

1. Prescreening survey for the aromatic elements of the study
2. Generalized Comfort Questionnaire (GCQ)
3. Ease Measure
4. Depression, Anxiety, and Stress Scale (DASS)
5. Post survey for aromatic elements of the study

\*\*Aroma Inhalers Used in this Study (See Appendix B)

1. Company supplying: Plant Extracts International <https://plantextractsinc.com/>
2. Bergamot essential oil is used
3. No direct contact with essential oil is anticipated
4. No ambient odor should be present as inhalers are factory sealed and enclosed in tamper resistant packaging

## Contents of Study Packets

1. Aroma inhaler
2. Aethereo®Stick Information Sheet
3. Cover letter (Appendix C)
4. Consent forms (2 copies)
5. Pre surveys (Comfort, Ease, and Stress)
6. Logbooks for Intervention or Control Groups (Appendix D)
7. Reminder paper (Appendix E)
8. 6 x 9 Postage paid return envelope
  - a. Post surveys (Comfort, Ease, Stress, Post Aroma)

## Prior to opening a Study Packet

1. In a private location, Enroller will determine eligibility for this study.
  - a. Inclusion criteria are as follows:
    - i. Older than 18 years of age
    - ii. Currently enrolled in treatment
    - iii. Have completed intensive phase 1 and wish to continue with treatment
    - iv. Alert & oriented
    - v. Able to provide written consent
    - vi. Able to read & write English
  - b. Exclusion criteria are as follows:
    - i. Diagnosed with severe mental illness
    - ii. Medical history of asthma
    - iii. Other serious respiratory disease
    - iv. Known allergy to citrus
2. In a private location, Enroller will prescreen using created survey tool (appendix A)
  - a. Use the prescreening survey provided
  - b. Read prescreening survey to participants and record answers
  - c. If not contraindicated by prescreening questions, allow participant to smell the aroma inhaler (3 inches from nose)
    - i. Record all reactions, “liked the smell”, “sneezed”, “said ‘yuck’” on the presurvey. Record “no negative reactions” as applicable (This is a vital component of aromatic research)
3. IF PARTICIPANT IS INELIGIBLE, thank them for their time, note on MLS that they were screened and why they were ineligible. Use the special section at the end of the MLS to make this notation. Do not use an Id # space. Write “ineligible” and the date across the top of the survey.
4. IF PARTICIPANT IS ELIGIBLE, file prescreening form in predetermined place and obtain a study packet in the order they are arranged (001-098)
  - a. Enter date and name of participant on the **Random Number Table (RNT)** sheet
5. Record Unique Identifier packet number on **Master Log Sheet (MLS)**
  - a. Use MLS to track Participants
  - b. This Unique Identifier number is already on every document in each packet

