## Common Terms List

Enroller – person who works with potential study participants to complete prescreening and explain study. This will be Investigator [name] or designee.

Participant – one who is willing and able to voluntarily participate in this study.

Aroma Inhaler – A small tube-shaped device about the size of a lipstick container. It contains a pure cotton wick. This wick is impregnated with pure essential oil. This is done at the manufacturer site. An Aethereo®Stick is used for this study. See appendix B for more information.

Aromatherapy – the use of aromas usually in the form of essential oils to impact a person's feelings of health and wellbeing.

Bergamot essential oil – is a citrus essential oil extracted from the rind of the fruit Bergamot (*Citrus bergamia*). The aroma is described as sharp, fruity, powdery, and refreshing. Research shows that chemical constituents found in Bergamot (linalool and linalyl acetate) may impact nerve receptors to bring about anxiolytic effects.

Randomized Controlled Trial (RCT) – a type of study where participants are randomly assigned to either an intervention or a control group. In this way, the risk of bias is decreased. Packets are distributed in an exact order and the Enroller does not pick which participants go into groups.

Random Number Table (RNT) – used to minimize risk of bias in studies. A table of numbers generated in an unpredictable, haphazard sequence.

Master Log Sheet (MLS) – Securely maintained Excel spreadsheet used to track assignment of participants to intervention or control groups. Also used to track those who are ineligible as determined by prescreening survey.

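### The randomization list is kept with the enrolment supplies and the Enroller writes on it before consent, so allocation is not shown to be concealed from the person who decides eligibility and obtains consent

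*Combined protocol and SAP*

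**What the plan says.** The section on supplies for enrolling participants lists, in one locked office, the Master Log Sheet, the tote of packets and the "Master Random Number Table (RNT) for randomization".

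Under Prior to opening a Study Packet, the Enroller determines eligibility and prescreens (steps 1-2). For those who fail, the Enroller is to "note on MLS that they were screened and why they were ineligible" (step 3). For those who pass, the Enroller takes the next packet in the 001-098 sequence (step 4), and then: "Enter date and name of participant on the Random Number Table (RNT) sheet" (step 4a). The packet number goes on the Master Log Sheet at step 5. Under Study Packet is Opened, the packet is opened at step 6, consent is signed at step 7 and pre-surveys are completed at step 8.

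The Common Terms List makes the Enroller an investigator or designee and defines the Master Log Sheet as a "Securely maintained Excel spreadsheet used to track assignment of participants to intervention or control groups". The only safeguard it states is this: "Packets are distributed in an exact order and the Enroller does not pick which participants go into groups".

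Contents of Study Packets includes a logbook specific to the arm. The Appendix D logbooks carry the arm's name at the top, so the packets are built by arm before anyone is enrolled.

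**The concern.** Concealment means that whoever decides who enters the trial cannot know the next assignment until the candidate is irrevocably in. Here one person decides eligibility, presents the study, obtains consent and handles both the randomization table and the assignment log. Fixed packet order stops that person choosing a packet for a given candidate. It does not stop knowledge of the next packet's arm from influencing which candidate is put forward, when, or how the study is described.

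The trial has little else to protect it. Control participants have no inhaler until they finish, so they know their arm, and comfort, ease and stress are all self-reported. If candidates who look likely to do well tend to meet an intervention packet, the comparisons in Hypotheses 1a and 1b are biased before treatment starts.

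**Working it through.** **1. The plan's own figure.** The Sample Size section states: "A total sample size of n=49 for intervention group and n=49 for control group is sought". With f = 0.25, m = 2 measurements, correlation 0.50 and alpha 0.05, the between-factors repeated-measures F test has noncentrality N·f²·m/(1+(m−1)·0.50) = 98 × 0.0625 × 2/1.5 = 8.17 on 1 and 96 df, and power 80.8%. At N = 96 power is 79.9%, so 98 is reproduced. The present point changes no sample size; 49 per arm is used below only for scale.

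**2. What the procedure implies about knowledge of the next arm.**
- Packets 001-098 each contain one arm's logbook, so a key from packet number to arm must exist.
- The only randomization list named is the Master RNT, and it is kept with the enrolment supplies.
- The Enroller writes on the RNT sheet for each eligible candidate. If the sheet shows arms, filling in one row exposes the next, before the next candidate is screened.
- For the current candidate, step 4a comes after the eligibility decision (steps 1-3) but before consent (step 7).
- No available section describes opaque packets, a separate list holder, or release of the arm only after consent and baseline. The sealing that is described concerns the inhalers.
- The remote process in Appendix G moves the pre-surveys online, mails the materials and has the sniff test done at home. It does not say who holds the list or when the arm is released.

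**3. Scale, with assumed inputs.** None of these assumptions is in the documents: the Enroller's impression correlates 0.5 with the outcome; there is no true effect; there are 49 per arm in a random order without blocking (none is stated); and steering means giving the intervention slot to the better prospect of two consecutive candidates.
- Only adjacent pairs with one slot of each arm can be steered. Their share is 2 × 49 × 49/(98 × 97) = 4802/9506 = 0.505.
- The expected gap in impression between the better and worse of two candidates is 2/√π = 1.128 SD. In outcome terms this is 1.128 × 0.5 = 0.564 SD.
- Bias = (share of discordant pairs steered) × 0.505 × 0.564.
- Noncentrality = bias × √(49/2) = bias × 4.95. The false-positive rate is from a two-sided 5% t test on a single post-score, 96 df.

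| Discordant pairs steered | Bias (SD) | Noncentrality | False-positive rate |
|---|---|---|---|
| 10% | 0.03 | 0.14 | 5.2% |
| 20% | 0.06 | 0.28 | 5.9% |
| 40% | 0.11 | 0.56 | 8.6% |

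This is a single post-score comparison, not the planned repeated-measures ANOVA. Baseline adjustment would remove only the part of the bias that baseline scores explain.

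**The case against.** The strongest reply is that the documents never say the Enroller can see an upcoming arm. The Common Terms List defines a random number table only as unpredictable numbers, step 4a asks only for a date and a name, and no layout is shown. That stands: sight of the next arm is an inference, though a strong one given the table's stated purpose and location.

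Other parts of the reply also stand, against readings that go too far:
- A reader might infer that the table is consulted during screening. Step 4a comes after the eligibility decision for that candidate. Only the Master Log Sheet is written on for people who fail screening, and a record of past assignments does not by itself reveal the next one.
- A reader might infer wide discretion from the sniff test. The Enroller is told to record reactions, verbatim, and the recorded reaction is not a listed exclusion. Judgement lies mainly in the alert-and-oriented criterion.
- A reader might infer that steering would leave no trace. Baseline scores, chart variables, screen failures and reasons for non-participation are all collected. They might reveal some steering, but not reliably.
- A reader might treat every adjacent pair as steerable. That would give 0.06, 0.11 or 0.23 SD and false-positive rates of 6%, 9% or 20%. With no blocking stated, only about half the pairs are discordant.

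It can also be said that the workflow has partly moved online, and that the consent pages and some appendices are not in the public text, so the present order of consent, pre-surveys and arm release cannot be fully judged. That limits certainty about current practice. It does not supply a concealment step in the text that can be read.

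**Conclusion.** The point holds in this form: the written procedure puts the randomization list with the person who decides eligibility and obtains consent, has that person write on it before consent, and offers fixed packet order as its only safeguard. Fixed order is not concealment. This goes beyond a missing detail, because the steps that are described place the list in the wrong hands.

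The documents do not show that the next arm is visible, or that any steering has occurred or is intended. The plan simply does not prevent it.

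Under the stated assumptions the effect is modest: about 0.03 to 0.11 SD, with a false-positive rate of about 5% to 9%. It depends on the assumed correlation of 0.5, the share of pairs steered, the absence of blocking and a single post-score comparison. The plan should be changed because the weakness is avoidable at little cost and could not be reliably corrected afterwards. If the list is in fact already held by someone who does not enrol, the protocol should say so and the enrolment steps should be corrected to match.

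**What to change.** 1. Remove the Master RNT from the enrolment supplies (item 3) and delete step 4a of Prior to opening a Study Packet.
2. Have an existing team member who does not enrol hold the RNT and the arm column of the Master Log Sheet. The protocol refers to co-investigators; that one of them does no enrolling is an assumption to confirm.
3. Limit the Enroller's log to ID, name and date.
4. Take the consent form and pre-surveys out of the arm-specific packet, or complete them online, as Appendix G already provides for the pre-surveys. Put the arm-specific materials in an opaque, sealed, numbered envelope. Sealing alone would not work while the consent form and pre-surveys sit inside the packet.
5. Release the arm for an ID only after eligibility, consent and pre-surveys are recorded. Mail arm-specific materials only after that point.

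The cost is protocol wording, one message to the list holder per enrolment, and some repacking. The sample size and the analysis are unchanged.
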